5.4 Provider Feasibility Sub Study Population

At each site, we will conduct a short feasibility Sub Study among the clinicians to determine the practicality of performing PCN (B-lactam) skin testing and oral challenge in the ambulatory STD setting (see secondary objective). Since this is an operational feasibility assessment, the sampled population will be clinicians who evaluate and treat patients at the participating clinic sites. The surveys will be administered once at the beginning of the study and again at the end. We estimate that there will be 15-30 eligible clinicians per site over the course of the study. Accounting for personnel turnover, we anticipate that the total sample will be no more than 150 individual respondents.

6 STUDY PROCEDURES/EVALUATIONS

6.1 Study Procedures

Operational implementation of study screening, enrollment and testing procedures will vary across the study sites. For example, depending on the operational considerations of the site, individuals may be screened in the waiting area, by the clinician and study staff during the actual clinic visit, or by study staff after the clinic visit has been completed. In some clinics it may be possible to perform the clinic visit procedures during the 30 to 60-minute \pm 10 minutes oral amoxicillin challenge observation period.

Clinical exams will be conducted as appropriate for the visit, but the clinic procedures are not included as part of the protocol. Study staff will emphasize to potential subjects that the expected time commitment involved in completing the study procedures is in addition to the time for the standard of care clinic procedures. A key operational study outcome is discovering if the time commitment involved is a barrier for both subjects and/or providers to allergy testing in ambulatory STD settings.

6.1.1 Screening

Screening will occur through mechanisms allowable at the individual sites including virtual screening and/or referral of individuals who have a prior history of reporting PCN allergy. If waiting room recruitment is permitted, study staff will approach potential subjects systematically, inform them that we are doing a study to optimize antibiotic use in ambulatory STD settings and ask if they were ever told they had an allergy to PCN or similar antibiotic. Subjects who report an allergy will be asked if they are interested in participating in the study. If the subject expresses interest, study staff will review the inclusion/exclusion criteria checklist to ensure the subject is eligible for enrollment. We will use standardized and Institutional Review Board (IRB)-approved screening scripts at all sites. All participants who are eligible for enrollment will be assigned a unique 5-digit participant number (PN). The same PN will be used if the participant is enrolled.

In some clinics, direct recruitment in the waiting room is not permitted. In these cases, we will post study advertising materials in the clinic waiting area promoting a study for individuals who have a history of PCN or B-lactam allergy. The clinic receptionist can also provide information to patients at time of registration. The recruitment materials will ask, “Do you have a history of penicillin or other antibiotic allergy?” or, “Have you ever been told that you are allergic to penicillin or other antibiotics?” Patients will be instructed to contact study staff in the clinic. Clinic providers may also refer patients to the study team.

Some clinics collect drug allergy information in the pre-visit medical history form. In these settings we will use a Health Insurance Portability and Accountability Act (HIPAA) Waiver of

Authorization to pre-screen potential subjects' medical records for drug allergy. Interviewers will confirm that the drug allergy is to PCN or B-lactam.

If a potential participant meets all inclusion/exclusion criteria but declines to consent or enroll in the study, study staff will record the reason they are not interested in participating in the study on a case report form (CRF). No identifying participant information will be collected unless the participant consents for enrollment.

6.1.2 Enrollment Visit (One Visit, Second Visit if Necessary)

After the participant provides informed consent, study staff will note the date the informed consent form (ICF) was signed and appropriate eligibility information on a CRF. Study staff will discuss basic demographic information with each participant and record the information on a CRF. Study CRFs will be maintained in the participant's research study record. Study staff will then administer the PCN (B-lactam) allergy history screening questionnaire to all participants using an iPad. Concomitant medication information will be collected.

All participants successfully screened, consented, and enrolled in the study will undergo the following procedures:

- Written, oral, or electronic informed consent to participate in this study
- Assessment of eligibility
- Enrollment in the study
- Assignment to allergy validation method
- Collection of demographic information (age, gender, race/ethnicity)
- Collection of contact information
- Administration of PCN (B-lactam) allergy history screening questionnaire
- Collection of concomitant medication information
- If antibiotic allergy history shows a low-risk history of PCN (B-lactam) allergy, option to receive skin test (if assigned to PST Group) or direct oral challenge (if assigned to DOC Group)

6.1.2.1 Subject Classification after Administration of PCN (B-lactam) Allergy History Screening Questionnaire (Appendix B)

Subjects will be classified as having a Low-Risk History or a Higher-Risk History for PCN allergy based on their responses to the PCN (B-lactam) allergy history screening questionnaire. These allergy history categories are defined based on positive responses to the questionnaire elements^{13,18,24,26}.

Low-Risk History

- Isolated GI upset (*diarrhea, nausea, vomiting, abdominal pain*)
- Chills (*rigors*)

- Headache
- Fatigue
- Itching (pruritus), self-limited
- Rash (including maculopapular rash)
- Hives (greater than 5 years ago)
- Flushing / redness
- Family history
- Patient denies allergy history but is in medical record

Higher-Risk History

- Angioedema or swelling of lip, tongue, or around eyes
- Wheezing / chest tightness moderate or severe shortness of breath
- Throat tightness which affected ability to breathe
- Hypotension without rapid recovery
- Arrhythmia / irregular heartbeat or palpitations
- Syncope / pass out / dizzy
- Anaphylaxis or sudden drop in blood pressure
- Hives (5 years or less)

Late effects (higher-risk events which occurred >24 hours after drug administration)

- Stevens-Johnson syndrome (Loss >10% of skin)
- Organ injury (liver, kidney)
- Low Platelets
- Drug reaction eosinophilia and systemic symptoms (rash with eosinophilia and organ injury)
- Acute generalized exanthem (rash with pustules)
- Dystonia or muscles became very stiff or very weak
- Serum sickness (rash with joint pain, fever, myalgia)
- Anemia
- Documented drug fever
- Erythema multiforme (rash with target lesions)
- Hives (5 years or less)

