stratification criteria to identify patients with reported allergy who have a high negative probability of being truly reactive. Low risk was identified as having GI reaction only (nausea, vomiting), having family history without a direct personal history, having had a history of taking a B-lactam drug and having an ill-defined allergic reaction in the distant past (>5 years).

Higher-risk groups were described as having the following symptoms within a year: hives or other pruritic rash, blister or bullous skin eruption after B-lactams, or IgE related symptoms (swelling/angioedema, syncope, dyspnea/wheezing or hypotension).

The smaller clinical trials found that if patients had low-risk symptoms only (i.e., no higher-risk symptoms), then direct oral challenge was safe. Furthermore, on an institutional basis, these protocols are being adopted in practice settings, and have been implemented in a number of large health systems such as Kaiser Permanente in California and Partners Health in Massachusetts. There have also been smaller reports of similar risk stratification being used to optimize pre-operative prophylaxis.

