2.2.3 Oral Challenge Approaches

The approaches recommended in the increasingly used algorithms, in many cases, advise bypassing skin testing and going directly to an oral challenge in low-risk patients. Two recent studies evaluated the impact and safety of this approach.

Iammatteo²³ instituted a direct oral challenge procedure in drug allergy clinics at Montefiore Hospital in the Bronx, NY. This study enrolled subjects >7 years old with non-life-threatening reported reactions to PCN. The exclusions included bronchospasm, anaphylaxis, non-IgE syndromes such as Stevens Johnson, cutaneous and/or mucosal blisters, hypersensitivity vasculitis, nephritis, hepatitis or anemia. Of 165 patients screened, 159 were enrolled and 156 completed a graded challenge without skin testing but which also incorporated a placebo. Of those challenged, 19 had reactions of which only 4 were determined to be allergy mediated and all were mild. It should be noted that this study skipped skin testing entirely.

Macy instituted a large PCN allergy management protocol at Kaiser Permanente San Diego.³ Between January 2017-December 2018, 806 patients had a direct oral challenge (no skin testing). Of these patients, 2 (0.2%) had an acute reaction, 9 (1.1%) had a delayed reaction; all were managed on-site with oral antihistamines or IM epinephrine; there were no hospitalizations. An additional 23 subjects (2.9%) had subjective reactions, such as mild nausea or headache.

Similarly, Blumenthal²⁴ implemented a risk-based algorithm in a large Boston based health system, and in a small study, directly challenged 83 low-risk patients in an outpatient setting. Of these patients, 3.6% experienced an immediate reaction (hives and rash), all resolved with treatment. In a larger antimicrobial stewardship-oriented intervention²⁵ which was performed in 5 acute care hospitals in 2016-17, patients with prior B-lactam allergy histories were evaluated using an EMR-based decision support tool and allergist consultation. A test dose of the prescribed B-lactam was administered in 1,045 instances to 942 patients with allergy histories considered low-risk. 96% of these cases did not have skin tests. Forty (3.6%) of patients had hypersensitivity reactions, 14 of which occurred within an hour of dosing. All were minor and treated successfully. Reactions were most frequent with late generation cephalosporins.

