6.1.2.2 Procedures After Defining Risk Category

Subjects classified with a low-risk history will progress to either skin testing (PST Group) or direct oral challenge (DOC Group), depending on which method of validating PCN allergy they are assigned. Subjects who meet the higher-risk classification will be advised that further elucidation of their allergy status will require a formal allergy evaluation. Referral resources will be provided.

All participants classified as low-risk and who meet additional qualification criteria to receive allergy testing (See Sec 6.1.3) will undergo the following procedures:

ASSIGNED TO PST GROUP

- Administration of skin test (prick test first and, if indicated, intradermal test)
- If skin test results are negative, option to receive oral challenge of 250 mg of amoxicillin
- Pre-oral challenge brief PE, assessment of vital signs and measurement of peak flow
- Administration of oral challenge
- Post-oral challenge brief PE, vital sign assessment and peak flow measurement

ASSIGNED TO DOC GROUP

- Pre-oral challenge brief PE, assessment of vital signs and measurement of peak flow
- Administration of oral challenge (first step) of 25 mg of amoxicillin, vital sign assessment and, if indicated, administration of oral challenge (second step) of 250 mg of amoxicillin
- Post-oral challenge brief PE, vital sign assessment and peak flow measurement

All participants will undergo the following procedures after allergy validation methods are offered or completed:

- Administration of subject acceptability survey on PCN testing procedures for all subjects who were offered skin testing (with or without oral challenge) or direct oral challenge
- Written documentation of PCN allergy testing results for all subjects who received skin testing (with or without oral challenge) or direct oral challenge to share with subject's medical care providers

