APPENDIX B: PCN (B-LACTAM) ALLERGY HISTORY SCREENING QUESTIONNAIRE

Section 1: Allergy History

- 1) How long ago was the reaction to the antibiotic?
 - a. < 6 months
 - b. 6 months-1 year
 - c. 2-5 years
 - d. 6-10 years
 - e. > 10 years
 - f. Don't remember / Unknown

- 2) What was the name of the drug you reacted to?
 - a. (Please list) _____
 - b. Don't remember / Unknown

- 3) How was the antibiotic administered?
 - a. Pill or Liquid by mouth
 - b. Injection (a shot) into a muscle or through a vein
 - c. Don't remember / Unknown

- 4) When did your allergic reaction to the antibiotic start?
 - a. Less than 1 hour after the first dose
 - b. Between 1 and 6 hours after the first dose
 - c. More than 6 hours, but less than 24 hours after the first dose
 - d. 24 hours or more after the first dose
 - e. Unknown

- 5) How many days did you receive your antibiotic treatment?
 - a. One day only
 - b. About _____ days of treatment
 - c. Don't remember / Unknown

- 6) People experience many different kinds of symptoms during an allergic reaction to an antibiotic. What were the symptoms of your allergic reaction? (OK to select more than one)
 - a. Can't remember (check only after reading entire list)

- b. Non-specific symptom(s) (e.g., "sick" "thought I was a goner" "high as a kite" "like I had the flu")

Responses to the symptoms listed below should be graded on a 5-point scale:

Don't Recall /None / Mild / Moderate / Severe

Low-Risk Allergy History

- a. Isolated GI upset (*diarrhea, nausea, vomiting, abdominal pain*)
- b. Chills (*rigors*)
- c. Headache
- d. Fatigue
- e. Itching (*pruritus*), self-limited,
- f. Rash (*including maculopapular rash*)
- g. Hives (greater than 5 years ago)
- h. Flushing / redness
- i. Family history
- j. Patient denies allergy history but is in medical record

Higher-Risk Allergy History: Skin Testing and Oral Challenge Contraindicated

- a. Angioedema or swelling of lip, tongue, or around eyes
- b. Wheezing / chest tightness moderate or severe shortness of breath
- c. Throat tightness which affected ability to breathe
- d. Hypotension without rapid recovery
- e. Arrhythmia / irregular heartbeat or palpitations
- f. Syncope / pass out / dizzy
- g. Anaphylaxis or sudden drop in blood pressure
- h. Hives (5 years or less)

Late Effect Symptoms (higher-risk events occurred >24 hours after drug administration)

- a. Stevens-Johnson syndrome (*Loss >10% of skin*)
- b. Organ injury (*liver, kidney*)
- c. Low Platelets

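### The risk-classification lists have no item for a past blistering or bullous drug reaction, so such a history could be recorded as low-risk rash and go on to skin testing or amoxicillin challenge

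*Protocol*

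**What the plan says.** Protocol 6.1.2.1 states the basis of the classification: "These allergy history categories are defined based on positive responses to the questionnaire elements". It then gives three lists.

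- **Low-risk (10 items).** One is "Rash (including maculopapular rash", with no limit on the type of rash, its severity or its date.
- **Higher-risk (8 items).** Angioedema, breathing and throat symptoms, circulatory symptoms, anaphylaxis, and hives within five years.
- **Late effects, also higher-risk (11 items).** The heading is "Late effects (higher-risk events which occurred >24 hours after drug administration". The skin-related entries include "Stevens-Johnson syndrome (Loss >10% of skin", pustular exanthem, erythema multiforme with target lesions, drug reaction with eosinophilia, and serum sickness.

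Appendix B Q6 repeats the lists and heads the main higher-risk block "Higher-Risk Allergy History: Skin Testing and Oral Challenge Contraindicated".

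The consequence is set in 6.1.2.2: "Subjects classified with a low-risk history will progress to either skin testing (PST Group) or direct oral challenge (DOC Group". Higher-risk subjects are referred for a formal allergy evaluation.

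Two background sections mention blistering. Section 2.1 describes higher-risk groups in published risk stratification and includes "blister or bullous skin eruption after B-lactams" among symptoms within a year. Section 2.2.3 reports that one direct-challenge study excluded, among other histories, "cutaneous and/or mucosal blisters".

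**The concern.** The questionnaire decides who is tested and who is referred. Blistering is a feature that the background names as a marker of higher risk, yet the instrument does not ask about it. The one item that would naturally absorb it is low-risk and unqualified.

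What is at stake is the safety of individual subjects. Someone with a blistering history could receive a skin test followed by 250 mg amoxicillin, or 25 mg then 250 mg amoxicillin directly, instead of an allergy referral. Observation after the 250 mg dose is 60 minutes in the PST group and 30 minutes in the DOC group (6.3.1, 6.3.2). If findings are then within limits, the subject is told that they have no allergy and gets written confirmation (6.3.3). No follow-up visit is required (6.4). Later symptoms reach the study only if the subject contacts staff (7.1.3). SAP 7.7 does tabulate adverse events beginning after 24 hours, but that would not show that the subject had a blistering history.

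**Working it through.** The plan states no figure on this point, so the check is a comparison of texts.

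**Step 1: item count.** In both 6.1.2.1 and Appendix B Q6, 0 of 8 higher-risk items and 0 of 11 late effects name a blister or bulla. The nearest entries are each tied to something else: skin loss above 10% for Stevens-Johnson syndrome, pustules for the exanthem, target lesions for erythema multiforme.

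**Step 2: background scheme against the trial's lists.**

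| Feature in the scheme described in 2.1 (within a year) | Place in 6.1.2.1 |
|---|---|
| Hives | Higher-risk if within 5 years, low-risk if older |
| Other pruritic rash | Self-limited itching and rash are low-risk |
| Blister or bullous eruption | No entry |
| Swelling or angioedema | Higher-risk |
| Syncope | Higher-risk |
| Dyspnea or wheezing | Higher-risk |
| Hypotension | Higher-risk |

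Every other feature is assigned somewhere. Blistering is in neither class, and no reason is given.

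**Step 3: what happens to such a subject.** Take a past blistering reaction with no listed higher-risk feature.

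- If staff mark the rash item, the subject is low-risk and 6.1.2.2 sends them to testing.
- If staff mark nothing, no stated rule assigns a class.
- Q6 has no write-in option, although Q7 and Q9 do, so Q6 offers no place to record the blistering itself.

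The first route seems the more natural one, but the documents do not say which would be taken.

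**Step 4: later checks.**

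- 6.1.3 covers current skin conditions and a rash that began in the week before the visit.
- The focused examination in 6.3 looks at the skin on the day.
- 7.1.1 goes back to the same high-risk questions.
- The clinical-judgment exclusion in 5.2.2 is discretionary. It belongs to the eligibility checklist reviewed at screening (6.1.1), and the questionnaire is given after enrollment (4.1).

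None of these asks about blistering in the past drug reaction.

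**Step 5: cost in precision if such subjects are referred.** Low-risk subjects: 95% of 1,000 = 950, from the 5% high-risk assumption in 8.2. Suppose, purely for illustration, that 10 are referred, leaving 940. The exact lower 95% limit for NPV is 1 minus the Clopper-Pearson upper limit for x reactors among n. The values of x are about 1% and 3% of 950.

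| Assumed reactors x | n = 950 | n = 940 |
|---|---|---|
| 10 | 98.07% | 98.05% |
| 28 | 95.77% | 95.72% |

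The limit moves by 0.02 and 0.05 percentage points. The 10 is not an estimate of how many subjects have this history.

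**The case against.** The strongest reply has four parts.

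1. *The severe named skin reactions are already higher-risk.* This stands. Stevens-Johnson syndrome, pustular exanthem, erythema multiforme, drug reaction with eosinophilia and serum sickness all lead to referral, as does blistering accompanied by angioedema, recent hives, organ injury or documented drug fever. Only blistering outside all of these is left.

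2. *The background is not the trial's scheme.* This also stands. A reader might infer that the protocol contradicts itself, and the text does not support that. Section 2.1 reports how others described higher-risk groups and limits the symptoms to the past year, so it says nothing about older blistering. The trial departs from that scheme elsewhere too, on hives and on itchy rash. The classification cites other sources, which cannot be seen here.

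3. *The late-effects heading is not a filter.* A reader might infer that a listed syndrome beginning within 24 hours would be disregarded. No rule says so. Onset time is asked separately in Q4, and a positive answer to a listed syndrome would reasonably count whatever its timing. The gap does not depend on that reading.

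4. *Staff see more than the tick boxes.* Q6 symptoms are graded up to severe, and Q7 records emergency care, admission and drug treatment. These answers could prompt caution, but neither sets the risk class. The qualification checklists named in 6.2 and 6.3 and the Manual of Procedures are not among the documents and might contain a further question. That limits the finding to the protocol as written.

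**Conclusion.** The gap is real and small. The lists do not name blistering, the low-risk rash item does not exclude it, and no later check in the protocol asks about it. Following the plan as written can therefore send a subject with such a history to skin testing or amoxicillin challenge.

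Two things remain unknown: whether staff would mark rash, and whether the omission was intended.

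The size cannot be stated. The documents give no frequency of past blistering reactions, so any count of affected subjects would be only an assumption. A reader might go on to infer a bias in the NPV or in the prevalence of reactivity. The documents do not support that either. The skin-test rates quoted in 2.1 concern all allergy histories, anaphylaxis and urticaria, and nothing ties them to blistering. No trial conclusion changes. This is a minor subject-safety point.

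**What to change.** 1. Add one item to the main higher-risk list in 6.1.2.1 and Appendix B Q6, outside the late-effects heading: *Blistering or bullous skin eruption, or mucosal blistering, with the antibiotic reaction (any onset time)*. Tying it to the antibiotic reaction avoids catching infectious lesions in STD patients.
2. Route a positive answer to allergy referral.
3. Restrict the low-risk item to *Rash without blistering or mucosal involvement*.
4. Set no date limit, as the cautious default. The clinical team may choose a look-back period if it gives a reason.

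The cost is one new line and one reworded line, in two places. No SAP change is needed. A few subjects may be referred instead of tested, and the loss of precision is negligible. If the omission was deliberate, a sentence giving the reason in 6.1.2.1 is the least that is needed, and the rash item should then say that it includes blistering rash.

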6.1.2.2 Procedures After Defining Risk Category

Subjects classified with a low-risk history will progress to either skin testing (PST Group) or direct oral challenge (DOC Group), depending on which method of validating PCN allergy they are assigned. Subjects who meet the higher-risk classification will be advised that further elucidation of their allergy status will require a formal allergy evaluation. Referral resources will be provided.

All participants classified as low-risk and who meet additional qualification criteria to receive allergy testing (See Sec 6.1.3) will undergo the following procedures:

ASSIGNED TO PST GROUP

- Administration of skin test (prick test first and, if indicated, intradermal test)
- If skin test results are negative, option to receive oral challenge of 250 mg of amoxicillin
- Pre-oral challenge brief PE, assessment of vital signs and measurement of peak flow
- Administration of oral challenge
- Post-oral challenge brief PE, vital sign assessment and peak flow measurement

ASSIGNED TO DOC GROUP

- Pre-oral challenge brief PE, assessment of vital signs and measurement of peak flow
- Administration of oral challenge (first step) of 25 mg of amoxicillin, vital sign assessment and, if indicated, administration of oral challenge (second step) of 250 mg of amoxicillin
- Post-oral challenge brief PE, vital sign assessment and peak flow measurement

All participants will undergo the following procedures after allergy validation methods are offered or completed:

- Administration of subject acceptability survey on PCN testing procedures for all subjects who were offered skin testing (with or without oral challenge) or direct oral challenge
- Written documentation of PCN allergy testing results for all subjects who received skin testing (with or without oral challenge) or direct oral challenge to share with subject's medical care providers

